HRP-503B – BIOMEDICAL RESEARCH PROTOCOL (2017-1)

Protocol Title: Comparison of pain perception and incidence of intravascular injection during transforaminal epidural steroid injection (TFESI) using 22 gauge vs 25 gauge needle.

Principal Investigator: [name]

Version Date: February 1, 2018

(If applicable) Clinicaltrials.gov Registration #: Not Available

INSTRUCTIONS

This template is intended to help investigators prepare a protocol that includes all of the necessary information needed by the IRB to determine whether a study meets approval criteria. **Read the following instructions before proceeding:**

1. Use this protocol template for a PI initiated study that includes direct interactions with research subjects. Additional templates for other types of research protocols are available in the system Library.
2. If a section or question does not apply to your research study, type “Not Applicable” underneath.
3. Once completed, upload your protocol in the “Basic Information” screen in IRES IRB system.

Section I: Research Plan

1. **Statement of Purpose:** State the scientific aim(s) of the study, or the hypotheses to be tested.

This is a pilot study to evaluate whether smaller bore 25 gauge needle can reduce the incidence of intravascular injection during TFESI compared to larger bore 22 gauge needle. Study will also evaluate any difference in patient pain perception between 2 needle types.

2. **Probable Duration of Project:** State the expected duration of the project, including all follow-up and data analysis activities.
1 year of enrolling subjects; 1 year of data analysis activities.
3. **Background:** Describe the background information that led to the plan for this project. Provide references to support the expectation of obtaining useful scientific data.
Transforaminal epidural steroid injection is very effective in placing injectate to ventral epidural space at the level of exact pathology, hence many practitioners prefer this technique over interlaminar approach, although there is no definitive evidence to suggest one is superior to the other. Rare but serious complications have been reported with TFESI including spinal cord infarction, hematoma, paralysis, and even death. Proposed mechanism of action behind these serious outcomes is inadvertent intravascular injections or the embolization of corticosteroid particulates. Although several needle types have been studied in the past, needle size has never been looked at in relation to intravascular uptake. It can be beneficial to know whether needle size plays a factor in intravascular uptake of injectate during TFESI. It can be hypothesized that 25 gauge needle due to its smaller diameter can potentially lead to less intravascular uptake. Practitioners tend to prefer 22 gauge needle for TFESI as it is easier to steer through tissue planes. There is also a notion that smaller 25 gauge needle tends to be less painful for patients.
4. **Research Plan:** Summarize the study design and research procedures using non-technical language that can be readily understood by someone outside the discipline. **Be sure to distinguish between standard of care vs. research procedures when applicable, and include any flowcharts of visits specifying their individual times and lengths.** Describe the setting in which the research will take place.
Prospective clinical trial. Goal is to recruit at least 250 patients. Patients will be given 2 forms to complete before and after the procedure. Patients will rate their pain before, during and after the procedure using VAS and/or similar ordinal scales. Patients will be blinded to what kind of needle being used. Practitioners will choose needle size randomly based on a computer-generated system. Live fluoroscopy to be utilized to confirm intravascular uptake on all cases. All practitioners to use similar approach for lumbar TFESI:
 1. S1 TFESI - target at superolateral aspect of posterior circular S1 foramen
 2. L1-L5 TFESI – target at supraneural ‘safe’ triangle (six o’clock position of the pedicle in the AP projection). May switch target to infraneural ‘Kambin’s’ triangle if injection cannot be safely administered with prior approach.
5. **Genetic Testing N/A #**
6. **Subject Population:** Provide a detailed description of the types of human subjects who will be recruited into this study.
Patients scheduled for lumbosacral TFESI at the Spine Center at YNHH Spine Center
7. **Subject classification:** Check off all classifications of subjects that will be specifically recruited for enrollment in the research project. Will subjects who may require additional safeguards or other considerations be enrolled in the study? If so, identify the population of subjects requiring special safeguards and provide a justification for their involvement. [Not Applicable]

#Children # Healthy #Fetal material, placenta, or dead fetus
#Non-English Speaking # Prisoners #Economically disadvantaged persons
#Decisionally Impaired # Employees #Pregnant women and/or fetuses
#Yale Students # Females of childbearing potential

NOTE: Is this research proposal designed to enroll children who are wards of the state as potential subjects?
Yes # No #

8. Inclusion/Exclusion Criteria: What are the criteria used to determine subject inclusion or exclusion?

Inclusion Criteria:

Patients scheduled for lumbosacral TFESI
LBP with or without leg pain

Exclusion Criteria:

Patients with contrast/local anesthetic allergy
Patients with pregnancy,
Coagulopathy,
Systemic infection,
Mental disability
Inability to provide informed consent.
Prior surgery
Severe Anxiety

9. How will **eligibility be determined, and by whom?**

The PI, [name] will determine eligibility

10. Risks: Describe the reasonably foreseeable risks, including risks to subject privacy, discomforts, or inconveniences associated with subjects participating in the research.

We are predicting that there may be increased risk for blood stream uptake of steroid particles with 22 gauge needle as opposed to 25 gauge needle. As mentioned earlier, this phenomenon has not been shown in any studies yet to date.

An inconvenience is lost time from filling out the questionnaire/consent form.

11. Minimizing Risks: Describe the manner in which the above-mentioned risks will be minimized.

Standard medical preparation and procedure will be utilized when giving the epidural injection, regardless of the needle gauge.

12. Data and Safety Monitoring Plan: Include an appropriate Data and Safety Monitoring Plan (DSMP) based on the investigator's risk assessment stated below. (Note: the HIC will make the final determination of the risk to subjects.)

a. What is the investigator's assessment of the overall risk level for subjects participating in this study? Minimal Risk

b. If children are involved, what is the investigator's assessment of the overall risk level for the children participating in this study? [Not Applicable]

c. Include an appropriate Data and Safety Monitoring Plan. Examples of DSMPs are available here <http://your.yale.edu/policies-procedures/forms/420-fr-01-data-and-safety-monitoring-plans-templates> for

- i. Minimal risk
- ii. Greater than minimal

The principal investigator is responsible for monitoring the data, assuring protocol compliance, and conducting the safety reviews at the specified frequency [*monthly*]. During the review process the principal investigator will evaluate whether the study should continue unchanged, require modification/amendment, or close to enrollment.

The principal investigator and the Institutional Review Board (IRB) have the authority to stop or suspend the study or require modifications.

This protocol presents minimal risks to the subjects and Unanticipated Problems Involving Risks to Subjects or Others (UPIRSOs), including adverse events, are not anticipated. In the unlikely event that such events occur, Reportable Events (which are events that are serious or life-threatening and unanticipated (or anticipated but occurring with a greater frequency than expected) and possibly, probably, or definitely related) or Unanticipated Problems Involving Risks to Subjects or Others that may require a temporary or permanent interruption of study activities will be reported immediately (if possible), followed by a written report within 5 calendar days of the Principal Investigator becoming aware of the event to the IRB (using the appropriate forms from the website) and any appropriate funding and regulatory agencies. The investigator will apprise fellow investigators and study personnel of all UPIRSOs and adverse events that occur during the conduct of this research project via email as they are reviewed by the principal investigator.

- d. For multi-site studies for which the Yale PI serves as the lead investigator: [Not applicable]
 - i. How will adverse events and unanticipated problems involving risks to subjects or others be reported, reviewed and managed? [not applicable]
 - ii. What provisions are in place for management of interim results? [not applicable]
 - iii. What will the multi-site process be for protocol modifications? [not applicable]

13. **Statistical Considerations:** Describe the statistical analyses that support the study design.

Literature evidence shows general incidence of intravascular uptake is 8.5% to 13% for TFESI depending on the level of injection. If one were to presume intravascular uptake rates for 22G vs 25G needle to be 11% versus 4%, 80% power to detect an effect at $p < .05$, 1-tailed, requires 125/group (250 total patients).

Section II: Research Involving Drugs, Biologics, Radiotracers, Placebos and Devices

If this section (or one of its parts, A or B) is not applicable, check off N/A and delete the rest of the section.

A. RADIOTRACERS **N/A**

B. DRUGS/BIOLOGICS **N/A**

C. DEVICES **N/A**

Section III: Recruitment/consent and assent procedures

1. **Targeted Enrollment:** Give the number of subjects: 250

- a. Targeted for enrollment at Yale for this protocol: 250
- b. If this is a multi-site study, give the total number of subjects targeted across all sites: [not applicable]

2. **Indicate recruitment methods below. Attach copies of any recruitment materials that will be used.**

# Flyers	# Internet/web postings	# Radio
# Posters	# Mass email solicitation	# Telephone
# Letter	# Departmental/Center website	# Television
# Medical record review*	# Departmental/Center research boards	# Newspaper
# Departmental/Center newsletters	# Web-based clinical trial registries	# Clinicaltrails.gov
# YCCI Recruitment database	# Social Media (Twitter/Facebook):	

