The investigator assures that the protected health information for which a Waiver of Authorization has been requested will not be reused or disclosed to any person or entity other than those listed in this application, except as required by law, for authorized oversight of this research study, or as specifically approved for use in another study by an IRB.

Researchers are reminded that unauthorized disclosures of PHI to individuals outside of the Yale HIPAA-Covered entity must be accounted for in the "accounting for disclosures log", by subject name, purpose, date, recipients, and a description of information provided. Logs are to be forwarded to the Deputy HIPAA Privacy Officer.

6. Process of Consent/Accent: Describe the setting and conditions under which consent/assent will be obtained, including parental permission or surrogate permission and the steps taken to ensure subjects' independent decision-making.

Patients will meet with the PI or any other designated consenting individual in a private clinic room, after they have been determined as a possible subject for the study. The study will be presented to the patient along with a copy of the informed consent. The patient and any other individuals as appropriate will have the opportunity to ask any questions they may have and all questions will be

answered completely. The patient will be given the opportunity to consider the trial and then sign if they are comfortable doing so.

7. **Evaluation of Subject(s) Capacity to Provide Informed Consent/Accent: Indicate how the personnel obtaining consent will assess the potential subject's ability and capacity to consent to the research being proposed.**
Individuals obtaining consent will evaluate the subject's ability to sign consent by evaluating their comprehension of the study procedures being presented and by the questions the subject asks regarding the study.

8. **Non-English Speaking Subjects: Explain provisions in place to ensure comprehension for research involving non-English speaking subjects. If enrollment of these subjects is anticipated, translated copies of all consent materials must be submitted for approval prior to use.**
Enrollment of non-English speaking participants is not anticipated.

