As a limited alternative to the above requirement, will you use the short form* for consenting process if you unexpectedly encounter a non-English speaking individual interested in study participation and the translation of the long form is not possible prior to intended enrollment? YES # NO #

Note* If more than 2 study participants are enrolled using a short form translated into the same language, then the full consent form should be translated into that language for use the next time a subject speaking that language is to be enrolled.

Several translated short form templates are available on the HRPP website (yale.edu/hrpp) and translated HIPAA Research Authorization Forms are available on the HIPAA website (hipaa.yale.edu). If the translation of the short form is not available on our website, then the translated short form needs to be submitted to the IRB office for approval via modification prior to enrolling the subject. *Please review the guidance and presentation on use of the short form available on the HRPP website.*

If using a short form without a translated HIPAA Research Authorization Form, please request a HIPAA waiver in the section above.

9. **Consent Waiver: In certain circumstances, the HIC may grant a waiver of signed consent, or a full waiver of consent, depending on the study. If you will request either a waiver of consent, or a waiver of signed consent for this study, complete the appropriate section below.**

#Not Requesting any consent waivers

#Requesting a waiver of signed consent:

Recruitment/Screening only (if for recruitment, the questions in the box below will apply to recruitment activities only)
Entire Study (Note that an information sheet may be required.)

Requesting a waiver of consent:

Recruitment/Screening only (if for recruitment, the questions in the box below will apply to recruitment activities only)
Entire Study

Section IV: Protection of Research Subjects

Confidentiality & Security of Data:

1. What protected health information (medical information along with the HIPAA identifiers) about subjects will be collected and used for the research? *Age, Sex, Medical Diagnosis, Pain Questionnaire*
2. How will the research data be collected, recorded and stored? *Data will be collected via the patients' medical record and patient questionnaire. Data will be stored in locked file cabinets, only accessible to members of the research staff.*

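### Does the plan need added text on keeping the needle draw, when it is released, and analysing patients by assigned needle?

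*Combined protocol and SAP*

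**What the plan says.** - **Allocation (Section I, item 4, Research Plan).** "Practitioners will choose needle size randomly based on a computer-generated system". The same item says that patients are blinded to the needle. It lets the practitioner move to a second anatomical target "if injection cannot be safely administered with prior approach". It has no corresponding allowance for changing the needle.
- **Eligibility and consent.** Section I, item 9 says the PI "will determine eligibility". Section III, item 6 places consent in a private clinic room: "The patient will be given the opportunity to consider the trial and then sign if they are comfortable doing so".
- **Data (Section IV, Confidentiality & Security of Data, item 2).** The sources named are the "medical record and patient questionnaire. Data will be stored in locked file cabinets". The computer system that makes the draw is not mentioned.
- **Compliance (Section I, item 12).** The PI is "responsible for monitoring the data, assuring protocol compliance".
- **Analysis (Section I, item 13, Statistical Considerations).** This is a sample-size statement only: 11% versus 4%, one-tailed .05, 80% power, 125 per group. It defines no analysis population.

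**The concern.** Three things that a randomised plan often states are absent: that the draw is kept, that it comes after consent and confirmed eligibility, and that it defines the groups compared.

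The setting makes the gap look relevant. The practitioner operates the draw and cannot be blind to the needle. Section I, item 3 (Background) gives a motive to depart from the draw in one direction: "Practitioners tend to prefer 22 gauge needle for TFESI as it is easier to steer through tissue planes". Section I, item 10 (Risks) gives one in the other: "We are predicting that there may be increased risk for blood stream uptake of steroid particles with 22 gauge needle".

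If practitioners switched needles in harder cases, and patients were then grouped by needle used, the comparison would no longer be the randomised one. Its error rate could rise or fall. Without a stored draw nobody could later show that it had been followed, and the PI's compliance duty would have nothing to compare for the trial's only intervention.

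**Working it through.** **1. The plan's own figure.** For 11% versus 4%, one-sided .05 and 80% power, the pooled formula is

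n = [1.645·√(2·0.075·0.925) + 0.842·√(0.11·0.89 + 0.04·0.96)]² / 0.07² = (0.6127 + 0.3107)² / 0.0049 ≈ 174.0, rounded up to 175 per group.

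The stated 125 does not reproduce. That is a separate matter and carries no weight here. It does explain why the power figures in step 5 start near 70% and not at 80%.

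**2. If the draw is followed.** Needle assigned equals needle used, so the choice of grouping cannot matter. Exact enumeration of a pooled z test (my assumption, since the plan names no test) with 125 per arm and 10% uptake in both arms gives a one-sided error of 5.18%.

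**3. What it takes to move that error.** Two events are needed: selective switching, and analysis by needle used. To size the effect I assume no needle effect, 10% overall uptake, 20% of cases difficult, and difficult cases at relative risk RR. None of the difficulty or switching inputs is in the documents.

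- Risk in easy cases = 0.10 / (0.8 + 0.2·RR). RR 2 gives 8.33% easy and 16.67% difficult; RR 3 gives 7.14% and 21.43%.
- Patients moved when 10% / 20% / 50% of one arm's difficult cases switch: 125·0.2·share = 2.5 / 5 / 12.5.

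Simulated one-sided error (400,000 trials per cell), grouped by needle used:

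| Direction | RR | 10% moved | 20% moved | 50% moved |
|---|---|---|---|---|
| 25G to 22G | 2 | 5.7% | 6.6% | 9.7% |
| 25G to 22G | 3 | 6.3% | 8.1% | 14.6% |
| 22G to 25G | 2 | 4.5% | 3.9% | 2.4% |
| 22G to 25G | 3 | 4.0% | 3.1% | 1.2% |

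At RR 1 the error stays between 5.0% and 5.2%. Grouped by assigned needle it is 5.1% to 5.3% in every cell.

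**4. Hand check of one cell (RR 2, 20% moved from 25G to 22G).**

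- Expected rate in the 22G-used group: (12.5 + 5·0.1667)/130 = 10.26%.
- Expected rate in the 25G-used group: (12.5 − 5·0.1667)/120 = 9.72%.
- The false difference is 0.53 points, against a standard error of √[0.09·(1/130 + 1/120)] = 3.80 points, so the shift is 0.14 standard errors.
- P(Z > 1.645 − 0.14) ≈ 6.6%, which agrees with the table.

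**5. What analysis by assigned needle would cost if switching occurred.** If a fraction f of 25G patients receive 22G, unrelated to risk, the 25G-assigned rate is 4% + 7%·f. Exact power at 125 per arm:

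| f | 25G-assigned rate | Difference (points) | Power |
|---|---|---|---|
| 0 | 4.00% | 7.00 | 70.5% |
| 2% | 4.14% | 6.86 | 68.5% |
| 4% | 4.28% | 6.72 | 66.4% |
| 10% | 4.70% | 6.30 | 60.3% |

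**6. Reading the text on the other two points.**

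- *Retention.* Section IV answers a confidentiality question. Item 1 there lists age, sex, diagnosis and the pain form, and leaves out intravascular uptake, which is the main outcome. The section is therefore not a full list of study variables, and its silence about the draw does not show that the draw is discarded. The medical record, a named source, may also hold the needle used.
- *Order.* Patients are identified, approached and consented in the clinic and are already booked for the injection. Needle selection is described among the procedural steps. The natural sequence is consent, then draw, and nothing points to an early draw.

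**The case for a change.** The best argument for a change is that a draw has to be saved when it is made. If it is lost, no later analysis can recover it, and the choice of groups is then open after results are seen. The practitioner knows the needle, the background reports a preference for 22G, some exclusions (severe anxiety, for example) call for judgement, and the PI may enrol patients from the PI's own clinic. A few sentences and one data field would cost almost nothing.

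Much of this is true. No section states any of the three points, and keeping the draw is good practice. But the argument shows only that the plan is brief. It does not show that the plan as written would mislead. The study cannot run without recording which needle each patient had, because that defines the comparison, and a system that generates the assignment is an obvious thing to keep. The error figures cover grouping by needle used only; no effect has been calculated for release before consent, or for redrawing. The largest entries, 14.6% and 1.2%, need half of the difficult cases in one arm to switch, all the same way, at three times the risk. Wording that calls the draw final could also be read as a rule on changing needles during a procedure, which is a clinical matter outside this review.

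**Conclusion.** No change to the plan is needed. The omissions are real, but they are details that a competent team fills in the ordinary way: keep the output of the randomisation system, consent before drawing, and compare patients by assigned needle. Nothing in the documents contradicts that practice, and the allowance for a change of target alone fits a draw that is meant to be followed.

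Followed as written, the effect on the result is nil (one-sided error 5.2% with either grouping). With assumed switching of 10% or 20% of difficult cases in one arm at relative risk 2, and grouping by needle used, the error runs from 3.9% to 6.6%, a shift of about 1.4 points or less with no settled direction. These figures rest on assumed uptake, difficulty, relative risk and switching shares, and on a pooled z test that the plan does not name. Evidence that needles were in fact switched, or an intention to group by needle used, would reopen the question.

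### Does the missing rule for counting intravascular uptake after a target switch leave the main outcome undefined?

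*Combined protocol and SAP*

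**What the plan says.** The Statement of Purpose (Section I, 1) asks whether the 25 gauge needle can "reduce the incidence of intravascular injection during TFESI compared to larger bore 22 gauge needle". The Background (Section I, 3) puts the question as "whether needle size plays a factor in intravascular uptake of injectate during TFESI". The Research Plan (Section I, 4) gives the means of detection: "Live fluoroscopy to be utilized to confirm intravascular uptake on all cases". The Risks item (Section I, 10) speaks of steroid particles reaching the blood stream.

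For L1-L5 the Research Plan lets the practitioner move from the supraneural to the infraneural target "if injection cannot be safely administered with prior approach". It gives S1 its own target and states no switch there.

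On allocation and blinding the Research Plan says "Practitioners will choose needle size randomly based on a computer-generated system" and "Patients will be blinded to what kind of needle being used". It does not say that anyone else is blinded.

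Statistical Considerations (Section I, 13) assumes uptake of 11% with 22G and 4% with 25G, one-tailed .05 and 80% power, and gives 125 patients per group. Section IV, item 2 names the medical record and the patient questionnaire as the data sources.

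**The concern.** Uptake is the only outcome with a sample size calculation, and the plan describes its measurement in one sentence. That sentence gives a method but no criterion for a positive image and no recorder. The target switch makes this look worse, because one patient can have two needle positions. The Background says "Proposed mechanism of action behind these serious outcomes is inadvertent intravascular injections", so vascular contrast is a plausible reason to move, although the plan does not say so.

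Take a patient whose contrast is vascular at the first position and clean at the second. The patient is an event if any uptake counts and a non-event if only the position where steroid is given counts. Intravascular injection could be read the second way and intravascular uptake the first.

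Three things would be at stake: inconsistent counting between practitioners, a rule picked after the results are known, and the loss of the very events that the trial is powered on. A practitioner who made the call would also know the gauge.

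**Working it through.** **Inputs.** From Section I, 13: 11% and 4%, 125 per group, one-tailed .05. Two quantities are not in the documents and are assumed:

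- *s*, the share of first uptakes followed by a second contrast injection at a new position;
- *t*, the share of no-uptake patients who also receive a second contrast injection.

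The uptake rate at a second position is taken to equal the rate at the first. No test is named, so both the pooled z test and Fisher's exact test are shown, by exact binomial enumeration.

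**The plan's own figure.** With pooled variance, n per group = [1.645 × √(2 × 0.075 × 0.925) + 0.842 × √(0.11 × 0.89 + 0.04 × 0.96)]² / 0.07² ≈ 174.02, rounded up to 175. The stated 125 does not reproduce. At 125 per group the exact power is 70.5% (Fisher 59.1%). That is a separate matter from the counting rule, and 70.5% is the baseline here.

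**Final position only.** Rate = p(1 − s) + s·p². For s = 0.50: 0.11 × 0.50 + 0.50 × 0.0121 = 0.0611 and 0.04 × 0.50 + 0.50 × 0.0016 = 0.0208. Multiplied by 125, unrounded, these give 7.6 and 2.6 events.

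| s | 22G / 25G rate | Expected events | Power, z (Fisher) |
|---|---|---|---|
| 0 | 11.0% / 4.0% | 13.8 / 5.0 | 70.5% (59.1%) |
| 0.25 | 8.6% / 3.0% | 10.7 / 3.8 | 62.1% (47.9%) |
| 0.50 | 6.1% / 2.1% | 7.6 / 2.6 | 52.3% (34.4%) |
| 0.75 | 3.7% / 1.1% | 4.6 / 1.4 | 42.1% (19.1%) |

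A row for s = 1 is left out. The switch is written for L1-L5 only, so a share of 100% through that rule would need every uptake to occur away from S1.

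**Any uptake during the procedure.** Rate = p + (1 − p)·t·p. A move made because of uptake changes nothing, since the patient is already an event. Only second injections in no-uptake patients matter.

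| t in 22G / 25G | 22G / 25G rate | Power, z (Fisher) |
|---|---|---|
| 0.10 / 0.10 | 12.0% / 4.4% | 73.4% (63.1%) |
| 0.25 / 0.25 | 13.4% / 5.0% | 77.5% (68.6%) |
| 0 / 0.10 | 11.0% / 4.4% | 64.9% (53.3%) |
| 0 / 0.25 | 11.0% / 5.0% | 56.6% (45.0%) |
| 0.25 / 0 | 13.4% / 4.0% | 87.0% (80.0%) |

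**Which reading the text supports.**

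- The purpose concerns the incidence of an event during the procedure. An event at the first position happened during the procedure.
- The Background uses the same frame and speaks of injectate, which does not confine the event to the steroid dose.
- The Research Plan has fluoroscopy confirm uptake in every case, with no restriction to the last position.
- Section I, 13 calls the event intravascular uptake and counts patients, so each patient contributes one result.
- The steroid-particle phrase in Section I, 10 describes a harm. It does not define an outcome.

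No section uses wording that limits the count to the final position.

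**The case for a change.** The strongest case for a change is that the rule really is absent. A few sentences would supply it, and an uptake seen at a first position but never written down may not be recoverable later. Calling the study a pilot does not fully answer this, because Section I, 13 powers a hypothesis test and several practitioners take part. The any-uptake reading is not immune to bias either. The Background says that 22G is "easier to steer through tissue planes". If 25G patients therefore need more contrast injections, they have more chances to show uptake, and the second table shows power moving in either direction when *t* differs by arm. It would be wrong to say that counting the first injection and counting any injection always come to much the same thing.

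Much of this stands as fact. The criterion, the recorder and the treatment of a switch are unstated, and a reader who knows the gauge is a limitation. What does not follow is that the plan uses a poor method. Any sensible rule fixed in advance would meet the concern, so the request is for detail and proposes no better design. The reading that costs much power is the one the text supports least. It also depends on uptake prompting the switch, which the plan does not say, and on a switching frequency that nobody has given. Recording is not wholly unaddressed, since fluoroscopy applies to every case and the medical record is a named data source.

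**Conclusion.** No change to the plan follows. The missing counting rule is a gap that an analyst would fill from the plan's own wording: any intravascular uptake seen during the procedure, once per patient. Under that reading a target switch made after uptake costs no events. The fall from about 70% to between 62% and 42% power (s from 0.25 to 0.75) belongs to a final-position rule that the documents nowhere state, at switching shares that they do not give. Those figures are illustrations and not an estimate of harm.

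Two limits remain for whoever interprets the results. The number of contrast injections may differ by gauge: with re-injection of 25% of no-uptake patients in one arm only, power is about 57% if that arm is 25G and about 87% if it is 22G. The person calling uptake may also know the needle; that effect is not sized, because the plan gives no misreading rate. The conclusion rests on the any-uptake reading and on first-position findings reaching the medical record. The failure of 125 per group to reproduce is a different question, and this point does not settle it.
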